### **Validity Substudy: Data Analyses and Power**

Data Analyses. We will perform data analyses for the validity substudy on the combined sample of intervention and control men. We assume that, despite our concerns about inclusion of the intervention group in the main study, the drug will not affect accuracy of diet recall.

The data analyses and power calculations described below emphasize the estimation of the reliability and validity correlation coefficients and their lower bounds. This is because the goal of the validity study is to estimate with reasonable confidence the magnitude of the validity and reliability coefficients rather than simply whether the correlation coefficients differ from zero.

The analyses will be based on standard techniques for analysis of validity and reliability studies. (39, 40) Specifically, we will assess the reliability of the food frequency questionnaire by comparing the measures from the one-year post-randomization administration of the FFQ to the measures from the two-year administration of the FFQ, using the intraclass correlation coefficient. We will calculate intraclass correlation coefficients and their lower confidence bounds for each of the dietary measures listed in Table 1. In addition, we will divide participants into quartiles of intake based on the first and second FFQs and compare these using weighted kappa.

We will assess the validity (bias and precision) of FFQ measures by comparing the dietary measure from the average of the year 1 and year 2 FFQs ( $X_1$ ) to the measure from the combined six (or at a minimum five) 24-hour dietary recalls completed between year one and year two ( $X_2$ ). We will assess systematic bias in the FFQ (versus the recalls) as the difference between the mean FFQ measure in the substudy subjects and the mean measure from the six, 24-hour dietary recalls:  $X_1 - X_2$ . We will compute a confidence interval around this mean difference based on a one sample t-test on the variable  $X_{i1} - X_{i2}$  computed for each subject  $i$ . We will assess precision as the Pearson correlation coefficient between  $X_1$  and  $X_2$ , and its lower 95% confidence bound. We will estimate

bias and Pearson correlation coefficients for each dietary measure in Table 1. Those nutrients that are positively skewed will be ln transformed for the computation of the Pearson correlation. We will also compute weighted kappas after categorizing subjects into quartiles based on  $X_1$  and quartiles of  $X_2$ .

### 3.10 Timeline

Data collection for the one-year visit begins in January 1995 and continues through December 1997. We will complete nutrient analyses of FFQs, clean the data and prepare analysis files between January and March of 1998. We will prepare the analysis plan and data documentation between April and May of 1998. The validity substudy will begin in Spring of 1995 and recruit participants evenly over one year. Validity substudy data collection will end in Spring of 1997, leaving adequate time for data analysis and manuscript preparation by the end of 1997.

## Appendix 19.8

### CAG Repeat Length Ancillary Study

#### A PROSPECTIVE COHORT STUDY OF CAG REPEAT LENGTH AND PROSTATE CANCER

##### 1.0 OBJECTIVES

###### 1.1 Primary Aim

- a. To assess the degree to which CAG trinucleotide repeat length is associated with an increased risk of prostate cancer. A shorter length is hypothesized to be associated with higher risk.

###### 1.2 Secondary Aims

- a. To investigate statistical models of prostate cancer risk as a function of CAG repeat length, ethnicity, race, family history, PSA level, age, arm, whether prostate cancer was discovered as a result of symptoms, and other potential explanatory factors.
- b. To obtain confirmatory data on the association of CAG repeat length and racial and ethnic groups.
- c. To obtain confirmatory data on the association (or lack thereof) of CAG repeat length and family history of prostate cancer.

## 2.2 Overview

[figure not shown]
This prospective study will look for associations between the CAG trinucleotide repeat length in the androgen receptor and the relative risk of developing prostate cancer. In addition, it will study the relationship between CAG repeat length and racial/ethnic groups, aggressiveness of disease, positive family history for prostate cancer and age of onset. Individuals enrolled on the PCPT provide an ideal population for such a prospective study. All participants in this study are initially determined to be disease free by standard PSA screening and digital rectal exam. The trial is of sufficient duration, and the participants old enough, so that the incidence of detecting prostate cancer should be significant. This will allow us to determine if a relationship exists between CAG repeat length and the risk of prostate cancer development. Additionally, due to the diversity of the patient population, the relationship between trinucleotide CAG repeat length and any racial or ethnic associated risk can be assessed.

No additional measures are being added to the PCPT. Frozen serum has been previously stored on all participants enrolled on the study. Using frozen serum, genomic DNA will be isolated and the CAG repeat region of the androgen receptor will be amplified using polymerase chain reaction (PCR). The CAG repeat length will be calculated based on comparison to known standards and confirmed on a percentage of samples by direct DNA sequencing of the amplified fragments.

## 2.3 Molecular Studies Influencing Current Clinical Approaches

The androgen receptor gene is located on the X chromosome (q11 - 12) and is composed of eight exons encoding three separate functional domains (Figure 1): the amino terminal transactivation domain, the DNA binding domain, and the steroid binding domain. The androgen receptor is activated by binding of either testosterone or DHT to the steroid binding domain in the cytoplasm followed by a loss of bound heat shock proteins. The activated receptor translocates to the nucleus where it recognizes and binds to 16 base pair imperfect palindromic sequences, called androgen responsive elements (ARE), found within the promoter region of a target gene. Binding to an ARE is mediated by two "zinc fingers" located in the DNA binding domain. The formation of either a homodimeric androgen receptor or a heterodimer with other nuclear hormone receptors may be required for transactivation activity either prior to or following DNA binding. Dimerization as well as interaction with accessory proteins may provide a level of specificity or selectivity in the target genes activated in a particular cell type. The transactivation domain interacts with the transcriptional machinery, and possibly other undetermined regions in the DNA, leading to changes in the transcriptional activity of a target gene. (10, 11) The androgen receptor is a 110 kDa protein belonging to a superfamily of ligand-responsive transcription regulators. Other members of this family include receptors for retinoic acid, triiodothyronine, vitamin D, and glucocorticoids. (12) Following activation by an agonistic ligand, androgen receptor stability is distinctly improved and serine/threonine phosphorylation occurs. (13) The physiological impact of these phosphorylated residues (serine 81, 94, and 650) is not clear, although some in vitro models have shown altered ligand binding transcriptional regulation upon phosphorylation. (14)

Fig. 1

## 2.4 CAG Repeat Region Background

The importance of hormones in regulating prostate cancer growth was established with the pioneering work of Huggins and Hodges in the 1940s. (16) Since that time, the critical role of the androgen receptor in mediating androgen hormone action has been increasingly recognized. In recent years, mechanistic studies of androgen receptor actions have shown that this protein functions as a ligand-dependent transcriptional regulator. (17) A number of studies demonstrate the importance of transcriptional regulation in the control of prostate growth and apoptosis. (18)

The androgen receptor, like all steroid hormone receptors, contains three functional domains. (17, 19) These domains include a steroid binding domain, a DNA binding domain, and a transactivation domain. Following the cloning of the androgen receptor cDNA, it was observed that the transactivation domain contains a number of CAG trinucleotide repeats encoding a homopolymeric stretch of glutamine residues. (19) This homopolymer region is polymorphic in the population, varying between 11 and 31 CAG repeats. (20)

Individuals with an expanded CAG repeat length (40 - 62 repeats) in the androgen receptor are afflicted with Kennedy's disease, a rare form of X-linked spinobulbar muscle atrophy. (21) Subsequent studies have demonstrated that men with Kennedy's disease have mild androgen insensitivity. (22) The length of the CAG repeat region is inversely related to the transcriptional activity of target genes. Mhatre et al. demonstrated that androgen receptors with 40 to 50 trinucleotide repeats exhibit decreased transcriptional activation from AREs in vitro. (23) In addition, Chamberlain et al. demonstrated that an increase in trinucleotide repeats decreased transactivation function in vitro. (24) It is speculated that a longer repeat length allows the formation of nucleosomes in this region leading to a decrease in transactivation. Deletion of the endogenous 25 CAG repeats in the human androgen receptor resulted in higher transactivation activity in vitro. Therefore, it has been hypothesized that a decreased CAG length would have an increased ability to activate target genes in the genome resulting in altered growth regulation and the development of prostate cancer. (25)

## 2.5 CAG Repeat Length and Prostate Cancer Risk

Differences in androgen receptor CAG repeat length have been linked recently to prostate cancer risk. (26 - 28) In a study of men participating in the Physicians Health Study, a comparison was made between 368 men with prostate cancer and 368 age-matched controls. In this study, men with high grade and/or high stage prostate cancer had a statistically significant higher proportion of short CAG repeats. In addition, initial observations in prostate cancer patients suggested an inverse relationship between CAG repeat length and cancer progression. (29, 30) These studies, although preliminary, are

the first to link a specific germline genomic polymorphism and prostate cancer risk. The implications of these studies are far reaching. The ability to stratify men according to prostate cancer risk using a simple genomic test could potentially alter current approaches to prostate cancer screening and/or prevention efforts.

a. CAG Repeat Length and Ethnic/Racial Differences

The CAG repeat length in the population is highly polymorphic. African-American males have a population average of 20.1 repeats, while caucasians average 22.0 repeats. Asians have a population average of 22.4 repeats. (26) Irvine et al. determined that the CAG repeat length is highly correlated with race and the frequency of prostate cancer within a population. (31) The prevalence of short repeat lengths (< 22) was highest (75%) in African-Americans, the group with the greatest risk for prostate cancer. Asians have the lowest risk of developing prostate cancer and the lowest prevalence of short CAG repeat lengths (49%). Non-Hispanic whites have an intermediate risk and a prevalence of 62% for < 22 CAG repeats.

b. CAG Repeat Length and Age of Onset

Many of the studies that have studied CAG repeat length have attempted to demonstrate a correlation with age of onset of the disease. Hardy et al. analyzed 109 men with histologically confirmed prostate cancer and found a positive correlation between shorter CAG repeat lengths (22 repeats) and younger age at diagnosis. (28) Stanford and colleagues also found that among men under the age of 60 years, there was shorter CAG repeat length and an increased risk of prostate cancer. However, in men between the ages of 60 - 64 years, shorter repeat lengths did not correlate with an elevated risk. (27)

c. CAG Repeat Length and Family History

Men with a family history of prostate cancer are at an increased risk of developing prostate cancer. Stanford et al. recently analyzed the CAG repeat length in 301 caucasian prostate cancer patients and 277 age/race-matched controls. (27) In this study, no association was found in men with no family history. Among men with either a father or brother affected with the disease, there was an increased risk associated with a shorter CAG repeat length (< 22 repeats).

### **3.0 STATISTICAL CONSIDERATIONS**

- 3.1 Introduction: The primary objective of this study (Section 1.1) and the secondary modeling objective (Section 1.2.1) cannot be analyzed until the clinical study is completed. The Data and Safety Monitoring Committee will not release data on incident cases discovered prior to the biopsy period, and full statistical power will not be available until all cases have been identified.

It is anticipated that there will be approximately 600 prostate cancer cases among the men randomized to the PCPT. Some of these cases will be identified prior to the scheduled biopsy. All 600 cases will have CAG repeat length assays. A sample of 1,200 controls (non-cases) will be identified and have CAG repeat length assays. Controls will either be

randomly selected from among men who have no evidence of prostate cancer, or be obtained using matching criteria. Potential matching factors include treatment arm, age at the time of randomization, and time on study. Consideration will also be given to using PSA level (adjusted PSA levels for finasteride arm patients) nearest to the time on study for the case as an additional matching factor for one of the controls. Higher PSA levels in controls may indicate the presence of undetected prostate cancer. Therefore, if CAG repeat length differences are smaller for the PSA matched controls then this would provide valuable additional information.

As implied in the previous paragraph, a significant methodological issue is that the existence of prostate cancer in cases will be known with high accuracy, whereas the absence of prostate cancer in controls is only presumed. This potential for misclassification in controls means that the results will have to be interpreted with caution, and innovations may be necessary (such as the PSA matching described above) in order to attempt to overcome the impact of this misclassification potential.

- 3.2 Objective 1.1: A sample size of 600 cases and 1,200 controls provides exquisite power for comparing the mean CAG repeat lengths between cases and controls. The standard deviation of CAG repeat length measurements is generally about 3.1. For the use of a *t* test for difference in the mean CAG repeat length between cases and controls, it is computed that as small as a 0.5 unit difference is detectable with a two-sided type I error probability of 0.05 and type II error probability of 0.1.
- 3.3 Objective 1.2a: The anticipated sample size should be adequate for most statistical modeling activities. All statistical modeling will be carried out in an exploratory mode and using standard protections against overfitting and overinterpretation. The primary modeling methodology will be logistic regression with the case/control status as the outcome and the explanatory variables mentioned in Section 1.2a as explanatory variables. The primary assessment will be to ascertain whether the CAG repeat length variable is additive to the other explanatory variables, including interactions where appropriate. In addition to logistic regression, more exploratory methods, such as regression trees, will be used.
- 3.4 Objective 1.2b: The analyses associated with secondary Objective 1.2b can be begun immediately because cancer incidence outcome will not be used. There will be an attempt to obtain results from 150 specimens for each ethnic or racial group. For the unadjusted comparison of CAG repeat length between two groups, under the conditions specified above to compute the sensitivity for the primary objective it is found that a CAG repeat length difference as small as 1.6 units is detectable. This is smaller than the previously reported differences between African-Americans and caucasians.
- 3.5 Objective 1.2c: The analyses associated with secondary Objective 1.2c can be begun immediately because cancer incidence outcome will not be used. There will be an attempt to obtain results from 500 specimens from those with a positive family history of prostate cancer and 500 controls (race matched) without a family history. For the unadjusted comparison of CAG repeat length between two groups under the conditions specified above to compute the sensitivity for the primary objective, it is found that a CAG repeat length difference as small as 0.6 units is detectable.
- 3.6 Data flow: The specimens will be identified at the Southwest Oncology Group Statistical Center, after which the tubes, labeled with accession number, will be shipped to [name] laboratory (address listed below) for CAG repeat length assay. The results of each

assay identified with the patient number will be transmitted to the Southwest Oncology Group Statistical Center for analysis according to the stated objectives. The PCPT data base will be used as the source of outcome and other explanatory variables for the analyses.

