#### 4.6 Preliminary Results

Using the current method of DNA isolation, we can obtain 140-1000 ng DNA from 200 μL serum with an A260:A280 ratio of 1.3 - 1.6. Of the patient sera we have examined to date, 29% had no detectable amplification products by ethidium bromide staining of the gels. Reactions that were negative for a product by ethidium bromide staining were reevaluated by staining with SYBR Green I (Molecular Probes, Eugene, OR). Using this stain, approximately 30% of the products that were previously undetectable were now easily seen. When products are run on denaturing gels and detected by silver staining, the yield is comparable to the SYBR Green I stain. Thus, the total recovery is 91%. In addition, we have not detected any artifacts that might be due to cross-contamination of DNA or reagents.

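### The CAG study lets men with no seven-year biopsy serve as controls, its 1.6-unit detectable difference should be about 1.2, and its assay-recovery figures do not agree with one another

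*Supplement*

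**What the plan says.** Appendix 19.8 plans a case-control comparison within the trial: about 600 cases, all to be assayed, and 1,200 controls.

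- **Control selection (Section 3.1).** Controls are to be "randomly selected from among men who have no evidence of prostate cancer, or be obtained using matching criteria". The choice is left open. On matching: "Potential matching factors include treatment arm, age at the time of randomization, and time on study". PSA is a further possibility, for one of the controls. The section concedes that "the absence of prostate cancer in controls is only presumed" and asks for cautious interpretation.
- **Modelling (Sections 1.2a and 3.3).** Risk is to be modelled "as a function of CAG repeat length, ethnicity, race, family history, PSA level, age, arm" and other factors, by logistic regression on case/control status.
- **Precision (Sections 3.2, 3.4 and 3.5).** With SD 3.1, two-sided type I error 0.05 and type II error 0.1, the detectable difference is given as 0.5 for 600 against 1,200 and 0.6 for 500 against 500. For 150 per racial or ethnic group, under the same conditions, "a CAG repeat length difference as small as 1.6 units is detectable".
- **Assay yield (Section 4.6).** On the first stain, 29% of sera showed no product. On restaining, "approximately 30% of the products that were previously undetectable were now easily seen". The text concludes "Thus, the total recovery is 91" (per cent).

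**The concern.** Having no evidence of cancer is not the same as having been examined for it. Main protocol Section 11.4 expects 20% of men to die, 15% to be lost and 5% to refuse before the seven-year biopsy, and nothing in Section 3.1 of the appendix keeps these men out of the control pool. The rest of the trial is stricter. The primary analysis (Section 11.9) uses men with a seven-year biopsy or an earlier histologically proven cancer, and the diet study (Appendix 19.7, Section 3.8) gives endpoint status only to such men. Unverified controls pull the CAG contrast towards zero, and they bring in a group that differs from the cases in survival and retention.

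The two numerical points concern whether the planning figures can be relied on. One detectable difference departs from its neighbours under identical conditions. The recovery percentage does not follow from the two percentages that precede it, and the sample-size text makes no allowance for failed assays.

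**Working it through.** **1. Share of controls without a seven-year biopsy**

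Inputs: 18,000 randomized, 60% biopsied, 40% not (Sections 11.1 and 11.4); about 600 cases (Appendix 19.8, Section 3.1).

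- Men with endpoint information: 18,000 x 0.60 = 10,800. Cases are 600/10,800, about 5.5%, so about 0.945 are biopsy-negative.
- Biopsy-negative men: 10,800 x 0.945 = about 10,200, for 1,200 control places.
- Unbiopsied share of the no-evidence pool: 0.40 / (0.40 + 0.60 x 0.945) = 0.40/0.967 = 0.41.
- Controls affected under unrestricted random sampling: 0.4137 x 1,200 = about 496.

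**2. Dilution**

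The prevalence of detectable cancer in these men is an assumption. I take 6% (the placebo planning rate in Section 11.8) to 13% (the yield among biopsied men with PSA below 4.0 in the screening series cited in Section 2.0). If misclassified controls have the same mean repeat length as cases, the difference shrinks by the misclassified fraction:

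- 0.4137 x 0.06 = 2.5%
- 0.4137 x 0.13 = 5.4%

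A true difference of 0.50 would appear as 0.50 x 0.975 = 0.49 down to 0.50 x 0.946 = 0.47.

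**3. Detectable differences**

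Formula: (1.960 + 1.282) x 3.1 x sqrt(1/n1 + 1/n2)

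| Section | n1 / n2 | Stated | Recomputed |
|---|---|---|---|
| 3.2 | 600 / 1,200 | 0.5 | 0.502 |
| 3.5 | 500 / 500 | 0.6 | 0.636 |
| 3.4 | 150 / 150 | 1.6 | 1.160 |

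The first two agree to one decimal; the third does not. A t-based calculation for 150 per group also gives 1.16. At a difference of 1.6, 150 per group have about 99% power, and 79 per group would be enough for 90%. Keeping n, alpha and sidedness as stated, no reading gives 1.6 at 90% power.

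**4. Recovery**

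- From the wording: 0.71 + 0.29 x 0.30 = 0.797, about 80%.
- 91% arises as 1 - 0.29 x 0.30 = 0.913, that is, if 30% of the initial failures remained undetectable. The rescue rate that 91% requires is (0.91 - 0.71)/0.29 = 69%.

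**5. Effect on Section 3.2**

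Only cases are limited in number; a control whose assay fails can be replaced.

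- 80% recovery: 478 cases and 1,200 controls give 10.05 x sqrt(1/478 + 1/1,200) = 0.54.
- 91% recovery: 546 cases and 1,200 controls give 10.05 x sqrt(1/546 + 1/1,200) = 0.52.

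Here 10.05 = 3.242 x 3.1.

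**The case against.** The appendix does not hide the misclassification. It calls it a significant methodological issue and offers PSA matching as a probe. The 41% applies only to unrestricted random sampling: matching on time on study to cases found at year seven would exclude many men who died or were lost early, and some men without a seven-year biopsy may have had an earlier negative one. A six-core biopsy also misses cancers, so biopsy-negative controls are not certainly cancer-free. All of this stands. It limits the gain but does not justify leaving the pool open when verified controls are plentiful.

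A reader might go further on four points that the documents do not support.

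- **That matching invalidates the analysis.** Matching is only an option, PSA would apply to one control, and the logistic model already contains arm, age and PSA. The CAG effect and its interactions stay estimable. What is lost is a valid main effect for each factor on which controls are matched, in modelling labelled exploratory.
- **That 80% is the true recovery.** The text does not show whether the 30% or the 91% is the slip.
- **That both samples shrink, to 478 and 956, with 0.56 detectable.** Failed control assays can be replaced. Retesting may rescue cases too: aliquots are split into 200 µL volumes (Section 4.1) and serum is banked at several visits (Study Calendar).
- **That 1.2 in Section 3.4 must be raised to 1.3 for assay loss.** The 150 there is a target for results obtained, so this would count the loss twice.

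The 1.6 figure also errs on the safe side. Both 1.16 and 1.6 lie below the reported African-American/caucasian difference of 22.0 - 20.1 = 1.9 repeats (Section 2.5a), so the conclusion in Section 3.4 is unaffected.

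**Conclusion.** The concern holds as a modest, cheaply mended weakness in an ancillary study; it does not touch the randomised comparison. Unless control selection is restricted, up to about 41% of controls would lack a seven-year biopsy and the CAG contrast would be diluted by about 2.5-5.4%. That range rests on the 40% loss planned in Section 11.4, random sampling from the whole no-evidence pool, an assumed 6-13% prevalence of detectable cancer in unbiopsied men, and misclassified controls resembling cases. The lack of comparability with men who died or were lost is a separate problem that the documents give no means to size.

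The 1.6 in Section 3.4 is wrong under its own conditions and conservative. The recovery figures in Section 4.6 contradict one another, and which is in error cannot be settled from the text. Under either reading, Section 3.2 is slightly optimistic because it assumes a result for every case.

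**What to change.** 1. In Section 3.1, draw the 1,200 controls from men with a negative seven-year biopsy, in line with Section 11.9 and the diet study. If matching is used, keep the matching factors in the model and do not interpret their main effects.
2. In Section 3.4, replace 1.6 with about 1.2 units (1.16).
3. In Section 4.6, reconcile the 29%, 30% and 91% against the laboratory record.
4. In Section 3.2, allow for failed case assays with controls replaced: about 0.54 units if recovery is 80%, about 0.52 if it is 91%.

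The cost is appendix wording and a different sampling list. Section 3.1 defers the case-control analysis until the trial is complete, so the rule can be set before controls are drawn. The small downside is that controls would represent men who stayed in the study and accepted biopsy, whereas cases found earlier need not have reached year seven. This should be stated as a limitation.
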